### 8.2.3 Safety Analysis

All safety analysis will be carried out on the safety population. The frequency tabulations of abnormal clinical laboratory values for the parameter will be presented by visit. Summary statistics for clinical laboratory parameters, ECG, physical examination and vital signs will be presented by visit.

All AEs observed during the study period will be listed. Incidence of all AEs reported during the study will be summarized using the Medical Dictionary for Regulatory Activities (MedDRA) (version 19 or higher) by body system, frequency, severity, seriousness and relationship to study drug and expectedness. Frequency and percentage of AEs occur during the course of study will be calculated and presented in the report. All AEs will be assessed for causality, severity and seriousness. The frequency tabulations of abnormal clinical laboratory values for the parameter will be presented by visit. Summary statistics for clinical laboratory findings and vital signs will be presented.

	Approved by: [name] [name]	Protocol No.: SARO.17.004.02.PROTOCOL Version No.: 2.0
---	------------------------------------	---

 Zydus Discovery DMCC	CLINICAL TRIAL PROTOCOL Saroglitazar Magnesium – Phase 2 SARO.17.004	CONFIDENTIAL Page 56 of 76
--	---	---

### 8.2.4 Demographic and Baseline Characteristics

Demographic characteristics and baseline characteristics will be summarized. Subject disposition and reasons for withdrawal will be presented as appropriate. Unless otherwise stated, all the continuous variables will be represented by n, mean, standard deviation, minimum, median and maximum. All the categorical variables will be presented as count and percentage.

### 8.2.5 Interim Analysis

No interim analysis will be performed.

### 8.2.6 Handling of Missing Data

Clarifications, wherever possible, will be obtained from the PI or designee for any missing data or for any illegible entry, unused or unauthenticated data.

[figure not shown]
Patients who are discontinued from the study will be excluded from PP analysis set. Any enrolled patient who are discontinued from the study for any reason and have at least one post-baseline efficacy measurement will be included in the mITT analysis set. LOCF method will be used as an imputation method for post-baseline missing values in mITT population set.

## 8.3 RANDOMIZATION

Patients will be randomly assigned in a 2:2:1 treatment allocation ratio to Saroglitazar Magnesium 2 mg and 4 mg and placebo, respectively. The randomization schedule will be generated to ensure the treatment balance by using SAS® software (Version: 9.4 or higher; SAS Institute Inc., USA).

## 8.4 DETERMINATION OF SAMPLE SIZE

This proof of concept study will include total 15 patients receiving from a multiple centers in a ratio of 2:2:1 to have 6 patients in Saroglitazar Magnesium 2 mg, 6 patients in Saroglitazar 4 mg and 3 patients in placebo arm for 24 weeks.

	Approved by: [name] [name]	Protocol No.: SARO.17.004.02.PROTOCOL Version No.: 2.0
---	------------------------------------	---

 Zydus Discovery DMCC	CLINICAL TRIAL PROTOCOL Saroglitazar Magnesium – Phase 2 SARO.17.004	CONFIDENTIAL Page 57 of 76
---	---	---

## 9 ADMINISTRATIVE MATTERS

The study will be carried out in compliance with the protocol, in accordance with the ICH Harmonised Tripartite Guideline for GCP and in accordance with applicable regulatory requirements.

### 9.1 ETHICS

[figure not shown]
#### 9.1.1 Institutional Committee Review and Communications

The study will not be initiated before the protocol and, informed consent and patient information form have been reviewed and have received approval/favorable opinion from a registered IEC/IRB. Should a protocol amendment be written that requires central IEC/IRB approval, the changes in the protocol will not be instituted until the amendment and revised informed consent (if appropriate) has been reviewed and received approval/favorable opinion from the IEC/IRB. A protocol amendment intended to eliminate an apparent immediate hazard to patients may be implemented immediately providing that the appropriate regulatory authorities and IEC/IRB are notified as soon as possible (no longer than 5 days) and an approval is requested. Protocol amendments only for logistical or administrative changes may be implemented immediately; however, both the IRB/IEC and the Regulatory Authorities will be notified as soon as possible.

The constitution of the IEC/IRB must comply with the requirements of the US Code of Federal Regulations. A list of the IEC/IRB members, with names and qualifications, will be requested. If such a list is unavailable, the PI or designee must provide the name and address of the IEC/IRB along with a statement from the IEC/IRB that it is organised according to GCP and the applicable laws and regulations. The IEC/IRB must also perform all duties outlined by the requirements of the regulatory agencies.

#### 9.1.2 Informed Consent and Subject Information

Prior to patient participation in the study, written informed consent will be obtained from each patient (or the patient's legally accepted representative) according to the regulatory and legal requirements of the participating country and site. Each signature must be dated by each signatory and the informed consent and any additional patient information form retained by the

	Approved by: [name] [name]	Protocol No.: SARO.17.004.02.PROTOCOL Version No.: 2.0

 Zydus Discovery DMCC	CLINICAL TRIAL PROTOCOL Saroglitazar Magnesium – Phase 2 SARO.17.004	CONFIDENTIAL Page 58 of 76
--	---	---

PI or designee as part of the study records. A signed copy of the informed consent and any additional patient information must be given to each patient or the patient’s legally authorised representative.

The patient must be informed that his/her medical records may be examined by authorised monitors or Clinical Quality auditors appointed by the Sponsor, by appropriate IEC/IRB members and by inspectors from regulatory authorities.

[figure not shown]
Should a protocol amendment be made, the patient informed consent form and patient information form may need to be revised to reflect the changes to the protocol. It is the responsibility of the PI to ensure that an amended consent form is reviewed and has received approval/favorable opinion from the IRB or IEC and that it is signed by all patients subsequently entered in the study and those currently in the study, if affected by the amendment.

## **9.2 DATA MANAGEMENT AND RECORD KEEPING**

### **9.2.1 Drug Accountability**

Drug supplies, which will be provided by the Sponsor, must be kept in a secure, controlled access storage area under the storage conditions defined by the Sponsor. A temperature log must be maintained to make certain that the drug supplies are stored at the correct temperature.

The PI and/or pharmacist must maintain records of the product’s delivery to the study site, the inventory at the site, the dispensation to each patient and the return to the Sponsor or alternative disposition of unused product(s). These records will include dates, quantities, batch/serial numbers, expiration dates (if applicable) and the unique code numbers assigned to the IP(s) and study participants. The PI or designee will maintain records that document adequately that the patients were provided the doses specified by the protocol and reconcile all IP(s) received from the Sponsor. At the time of return to the Sponsor, the PI or designee must verify that all unused or partially used drug supplies have been returned by the study participants and that no remaining supplies are in the PI or site’s possession.

	Approved by: [name] [name]	Protocol No.: SARO.17.004.02.PROTOCOL Version No.: 2.0
---	------------------------------------	---

## 9.2.2 Data Management

### 9.2.2.1 Data Handling

Data will be recorded by the PI or designee into eCRFs and reviewed by the study monitor during monitoring visits. The study monitor will verify data recorded in the electronic data capture (EDC) system against source documents. All corrections or changes made to any study data must be appropriately tracked in an audit trail in the EDC system. An eCRF will be considered complete when all missing, incorrect and/or inconsistent data has been accounted for and the eCRF is signed by the PI.

### 9.2.2.2 Computer Systems

Data will be processed using a validated computer system conforming to regulatory requirements.

### 9.2.2.3 Data Entry

Data must be recorded in to the EDC system in a timely manner as the study is in progress. All site personnel must log into the system using their secure user name and password in order to enter, review, or correct study data. These procedures must comply with the appropriate international regulations. All passwords will be strictly confidential.

[figure not shown]
### 9.2.2.4 Medical Information Coding

For medical information, the following thesauri will be used:

- Latest version of MedDRA for adverse events and medical history and
- WHO Drug Dictionary for prior and concomitant medications.

### 9.2.2.5 Data Validation

Validation checks programmed within the EDC system, as well as supplemental validation performed via review of the downloaded data, will be applied to the data in order to ensure accurate, consistent and reliable data. Data identified as erroneous, or data that are missing, will be referred to the investigative site for reconciliation/resolution through data queries.

The eCRFs must be reviewed and approved/signed by the PI.

### 9.2.3 Source Documents

Source documents provide evidence for the existence of the patient and substantiate the integrity of the data collected. Source documents are filed at the PI’s site. Data reported on the eCRFs must be consistent with the source documents or the discrepancies must be explained.

[figure not shown]
The PI or designee may need to request previous medical records from another institution, depending on the study; also, current medical records – not just shadow charts – must be available.

The following data to be reported on the eCRF should be included and derived from source documents:

1. Subject identification (subject number, gender, date of birth/age)
2. Subject participation in the study (subject number, date informed consent given)
3. Dates of subject’s visits
4. Medical history
5. Medication history
6. AEs (onset and end)
7. SAEs (onset and end)
8. Originals or copies of laboratory results: All laboratory reports must be reviewed by the Investigator and/or his/her designee; any abnormal findings should be addressed.
9. Conclusion of patient’s participation in the study.

### 9.2.4 Direct access to Source Data/Documents

The PI/ Institution will permit study-related monitoring, audits, IRB/IEC reviews and regulatory inspections by providing direct access to all related source data/documents. Case report forms and all source documents, including progress notes and copies of laboratory and medical test results must be available at all times for review by the Sponsor’s clinical trial monitor(s), auditor(s) and inspection by applicable regulatory authorities. The on-site monitor will review all eCRFs and ICFs. The accuracy of the data will be verified by reviewing the documents described in *Section 9.2.3*.

 Zydus Discovery DMCC	CLINICAL TRIAL PROTOCOL Saroglitazar Magnesium – Phase 2 SARO.17.004	CONFIDENTIAL Page 61 of 76
--	---	---

All ECG's will be conducted locally. A photocopy should be made of the ECG and assessment of clinical significance should be conducted by site staff personnel delegated to do so.

### 9.2.5 Trial Monitoring

[figure not shown]
It is the responsibility of the PI to ensure that the study is conducted in accordance with the protocol, ICH GCP and applicable regulatory requirements and that valid data are entered into the eCRFs.

To achieve this objective, the study monitor's duties are to aid the PI, and, at the same time, the Sponsor in the maintenance of complete, legible, well-organized and easily retrievable data. Before the enrollment of any subject in this study, the Sponsor or their designee will review with the PI and site personnel the following documents: protocol, Investigator's Brochure, eCRFs and procedures for their completion, informed consent process and the procedure for reporting SAEs. The PI will permit the Sponsor or their designee to monitor the study as frequently as deemed necessary to determine that data recording and protocol adherence are satisfactory. During the monitoring visits, information recorded on the eCRFs will be verified against source documents and requests for clarification or correction may be made. After the eCRF data is entered by the site, the monitor will review the data for safety information, completeness, accuracy and logical consistency. Computer programs that identify data inconsistencies may be used to help monitor the clinical study. If necessary, requests for clarification or correction will be sent to PIs. The PI and his/her staff will be expected to cooperate with the monitor and provide any missing information.

All monitoring activities will be reported and archived. In addition, monitoring visits will be documented at the investigational site by signature and date on the study-specific monitoring log.

### 9.3 QUALITY AUDITS

Quality audits of this study may be conducted by the Sponsor or Sponsor's designees. The quality auditor must have access to all medical records, the study-related files and correspondence, and the informed consent documentation that is relevant to this clinical study.

	Approved by: [name] [name]	Protocol No.: SARO.17.004.02.PROTOCOL Version No.: 2.0
--	------------------------------------	---

 
Zydus Discovery DMCC
	
CLINICAL TRIAL PROTOCOL  Saroglitazar Magnesium – Phase 2  SARO.17.004
	
CONFIDENTIAL  Page 62 of 76

---	--	--

## 9.4 PROCEDURES

### 9.4.1 Adverse Events

All AEs occurring during the course of the clinical study from the signing of the informed consent onwards will be collected, documented and reported to the Sponsor by the PI or designee according to the specific definitions and instructions detailed in this section. The Common Terminology Criteria for Adverse Event (CTCAE) (Version 4.03 or higher) system will be used for reporting and grading AEs.

An AE is defined as any untoward medical occurrence in a clinical investigation subject administered a pharmaceutical product and which does not necessarily have a causal relationship with this treatment.

Any medical condition already present at screening should not be reported as an adverse event unless the medical condition or signs or symptoms present at baseline changes in severity or seriousness at any time during the study. In this case, it should be reported as an adverse event.

Clinically significant abnormal laboratory or other examination (e.g. electrocardiogram) findings that are detected during the study or are present at screening and significantly worsen during the study should be reported as AEs. The PI will exercise his or her medical and scientific judgment in deciding whether an abnormal laboratory finding or other abnormal assessment is clinically significant. Clinically significant abnormal laboratory values occurring during the clinical study will be followed until repeat tests return to normal, stabilize, or are no longer clinically significant. Any abnormal test that is determined to be an error does not require reporting as an AE.

### 9.4.2 Serious Adverse Events

A serious adverse event is any adverse event occurring at any dose or during any use of Sponsor's product that:

1. Results in death;
2. Is life threatening;
3. Results in persistent or significant disability/incapacity;
4. Results in inpatient hospitalization or prolongs an existing inpatient hospitalization;

	
Approved by: [name] [name]
	
Protocol No.: SARO.17.004.02.PROTOCOL Version No.: 2.0

--	--	---

 Zydus Discovery DMCC	CLINICAL TRIAL PROTOCOL Saroglitazar Magnesium – Phase 2 SARO.17.004	CONFIDENTIAL Page 63 of 76
--	---	---

5. Is a congenital anomaly/birth defect;
6. Is another important medical event that may not result in death, be life-threatening, or require hospitalization may be considered serious when, based upon appropriate medical judgment, they may jeopardize the patient or subject and may require medical or surgical intervention to prevent one of the outcomes listed above.

**Serious adverse event reporting-procedures for Investigator:**

[figure not shown]
**Initial Reports:**

Any SAE, or follow-up to a serious adverse event, including death due to any cause that occurs to any subject from the time the consent is signed through 7 days following cessation of treatment, whether or not related to the Sponsor's product, must be reported to the Sponsor within 24 hours of the knowledge of the occurrence to investigational site.

Additionally, any SAE, considered by the PI or designee, who is a qualified physician to be related to the Sponsor's product that is brought to the attention of the PI or designee at any time outside of the time period specified in the previous paragraph also must be reported immediately to the Sponsor.

To report an SAE, complete the SAE form electronically in the EDC system for the study. When the form is completed, the CRO/Sponsor Safety personnel will be notified electronically. If the event meets serious criteria, and, it is not possible to access the EDC system, send an email to CRO/Sponsor or call the CRO/Sponsor SAE hotline (phone number listed below) and email the completed SAE form/information to CRO/Sponsor (email listed below) within 24 hours of awareness. When the EDC system becomes available, the SAE information must be entered within 24 hours of the system becoming available.

Safety Contact Information:

	Approved by: [name] [name]	Protocol No.: SARO.17.004.02.PROTOCOL Version No.: 2.0

 Zydus Discovery DMCC	CLINICAL TRIAL PROTOCOL Saroglitazar Magnesium – Phase 2 SARO.17.004	CONFIDENTIAL Page 64 of 76
---	---	---

### **Follow-Up Reports**

All patients with serious adverse events must be followed up for outcome. Within 24 hours of receipt of follow-up information, the PI or designee must update the SAE form electronically in the EDC system and submit any supporting documentation (e.g., subject discharge summary or autopsy reports) to Sponsor Clinical Safety via fax or e-mail. If it is not possible to access the EDC system, refer to the procedures outlined above for initial reporting of SAEs.

#### **9.4.3 Follow-up of Adverse Events**

All AEs experienced by a subject, irrespective of the suspected causality, will be monitored until the AE has resolved, any abnormal laboratory values have returned to baseline or stabilized at a level acceptable to the PI and Medical Expert, until there is a satisfactory explanation for the changes observed, until the subject is lost to follow-up or until the subject has died.

#### **9.4.4 Evaluating Adverse Events**

Each AE will be assessed by the PI or a medically-qualified investigator with regard to the following categories:

[figure not shown]
##### **9.4.4.1 Severity**

The PI or designee will provide an assessment of the severity of each AE by recording a severity rating on the appropriate AE reporting page of the subject's eCRF. The Common Terminology Criteria for Adverse Event (CTCAE) (Version 4.03 or higher) system will be used for reporting and grading AEs severity of events not classified in CTCAE will be assessed according to the following scale:

Mild: Event is usually transient and easily tolerated, requiring no special treatment and causing no disruption of the subject's normal daily activities.

Moderate: Event introduces a low level of inconvenience or concern to the subject and may interfere with daily activities, but is usually improved by simple therapeutic measures. Moderate experiences may cause some interference with functioning.

Severe: Event interrupts the subject's normal daily activities and generally requires systemic drug therapy or other treatment. Severe events are usually incapacitating.

	Approved by: [name] [name]	Protocol No.: SARO.17.004.02.PROTOCOL Version No.: 2.0

 Zydus Discovery DMCC	CLINICAL TRIAL PROTOCOL Saroglitazar Magnesium – Phase 2 SARO.17.004	CONFIDENTIAL Page 65 of 76
--	---	---

#### 9.4.4.2 Causality

For all AEs, the PI or designee will provide an assessment of causal relationship to study drug. The causality assessment must be recorded on the appropriate AE reporting page of the subject's eCRF.

Causal relationship will be classified according to the following criteria:

- Unrelated
- Possibly related: Suggests that the association of the AE with the study drug is unknown. However, the AE is not reasonably supported/explained by other conditions.
- Probably related: Suggests that a reasonable temporal sequence of the AE with study drug administration exists and, based upon the PI's clinical experience, the association of the AE with study drug seems likely.
- Definitely related: Suggests that a causal relationship exists between the study drug and the AE, and other conditions (concomitant illness, progression or expression of the disease state, reaction to concomitant medication) do not appear to explain the AE.
- Unknown

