### 5.8.3 Permitted Concomitant Medications

With the exception of excluded concomitant medications, other medications that subjects have been taking at stable dosages for at least 3 months prior to biopsy, i.e., statins, drugs for glycemic control and hypertension will be permitted as concomitant medications. To the extent possible, subjects should continue with their current regimen of medication without any change throughout the study.

[figure not shown]
Allowed over-the-counter medications include acetaminophen (maximum 1 gram/day), ibuprofen (maximum 800 mg/day) or naproxen (maximum 440 mg/day) or antacids such as H2 receptor blockers or proton-pump inhibitors for shorter duration as per Investigator discretion.

The PI should be alerted if, during the course of the study, a subject requires a new medicine or therapy or a change to an established dosing regimen. All medications that target NAFLD or NASH, or have been suggested to target the underlying causes of NAFLD or NASH, should be reviewed and agreed on by the PI, Medical Expert and Sponsor before being taken by the subject.

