#### 9.4.5 Expected Adverse Events

Adverse events reported by 2% or more subjects treated with Saroglitazar Magnesium during the double-blind, active-controlled study with Pioglitazone as the comparator regardless of causality

	Approved by: [name] [name]	Protocol No.: SARO.17.004.02.PROTOCOL Version No.: 2.0
--	------------------------------------	---

 Zydus Discovery DMCC	CLINICAL TRIAL PROTOCOL Saroglitazar Magnesium – Phase 2 SARO.17.004	CONFIDENTIAL Page 66 of 76
--	---	---

included gastritis and asthenia. In the double-blind placebo controlled study, AEs reported by 2% or more subjects treated with Saroglitazar Magnesium included gastritis, dyspepsia, pyrexia and pain. The details of AE(s) experienced during the Saroglitazar studies are mentioned in the IB. Principal Investigator(s) are advised to provide protocol education for patients and caregivers for potential symptoms of adverse effects that should be reported to the site/PI, such as skeletal muscle pain, weight gain, peripheral edema, shortness of breath, hypoglycaemia, etc.

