7.3.2 Adverse Events

The applicable definition of an Adverse Event (AE) is in the study protocol section 9.4. A treatment-emergent AE (TEAE) is an event not present prior to exposure to study drug or any pre-existing event that worsens following exposure to study drug. The period for treatment-emergent AE analysis starts from the first exposure to the study drug until the patient exits the study. Adverse events (AEs) will be coded using MedDRA to give a preferred term and a SOC term for each event.

Descriptive summaries (frequencies and percentages) for specific TEAEs will be presented by system organ class and preferred term according to the Medical Dictionary for Regulatory Activities (MedDRA Version 19.1) dictionary. In addition to an overall presentation of all TEAEs, reports will be generated for special classes of TEAEs such as study drug related TEAEs, serious TEAEs, Maximum severity and TEAEs resulting in treatment discontinuation. These reports will be supported by individual patient listings, as necessary.

Adverse events will be counted by the number of events as well as the number of patients. For the summaries which count the number of patients, multiple TEAEs with the same MedDRA preferred term within the same subject will only be counted once.

Document Title:	Statistical Analysis Plan		
Version Number:	1.0	Date:	31 Mar 2020
Protocol Number:	SARO.17.004	Sponsor Name:	Zydus Discovery DMCC

Only patient listings will be provided for AEs that occur after signing informed consent but prior to exposure to investigational product. These listings will comprise all events occurring during this period in any subject who consented to participate in the study.

These listings will at least contain but not limited to information such as onset and resolution times, maximum severity, causal relationship to study treatment and action taken.

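### Protocol 9.4.4.2 bars Possibly related, the weakest related level, for AEs that another condition could explain, so an AE with an uncertain drug link and a rival explanation meets no related definition

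*Protocol*

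**What the plan says.** Protocol 9.4.4.2 requires the PI or designee to classify every AE as Unrelated, Possibly related, Probably related, Definitely related or Unknown. Unrelated and Unknown have no definition. The three related levels read as follows.

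- **Possibly related** has two parts: "Suggests that the association of the AE with the study drug is unknown", followed by "However, the AE is not reasonably supported/explained by other conditions".
- **Probably related** asks for plausible timing relative to dosing and for a judgement, from clinical experience, that "the association of the AE with study drug seems likely". It does not mention other explanations.
- **Definitely related** asks for a causal relationship and adds that other conditions, among them concomitant illness, disease progression and a "reaction to concomitant medication) do not appear to explain the AE".

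The classification feeds two outputs. Protocol 8.2.3 summarises AEs "by body system, frequency, severity, seriousness and relationship to study drug and expectedness". SAP 7.3.2 plans reports for "special classes of TEAEs such as study drug related TEAEs". The SAP neither redefines the levels nor says which of them count as study drug related.

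**The concern.** A causality scale normally keeps its weakest related level for events where the drug may be responsible but something else may be too. Here that level is closed to those events, while the level above it is open to them.

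The protocol's own content shows how the case can arise. Section 9.4.5 lists symptoms for patients to report, "such as skeletal muscle pain, weight gain, peripheral edema, shortness of breath, hypoglycaemia". Section 5.8.3 allows background treatment: "statins, drugs for glycemic control and hypertension will be permitted as concomitant medications". Suppose a patient on a permitted glucose-lowering drug has hypoglycaemia, and the PI regards that drug as a reasonable explanation but cannot exclude study drug. The wording then bars Possibly related. The premise that the background drug could explain the event is ordinary clinical judgement and is not stated in the documents.

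What is at stake is the completeness of the drug-related safety display in a trial for which safety is a stated objective.

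**Working it through.** The plan gives no figure on this point, so the check is a logical one. The inputs are the three related definitions in Protocol 9.4.4.2.

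**Step 1. Set the definitions side by side.**

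| Level | Required link to study drug | Must other explanations be absent? |
|---|---|---|
| Possibly related | Unknown | Yes |
| Probably related | Plausible timing and a likely association | Not addressed |
| Definitely related | Causal relationship | Yes |

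The exclusion applies at 2 of the 3 related levels, the weakest and the strongest, but not at the middle one.

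**Step 2. Test AEs against the definitions.**

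- *AE 1: uncertain link, another reasonable explanation.* It fails Possibly on the exclusion clause. It fails Probably because the association does not seem likely. It fails Definitely on both parts. It fits 0 of 3 related levels, so only Unrelated and Unknown remain.
- *AE 2: uncertain link, no other explanation.* It fits Possibly.
- *AE 3: plausible timing, likely link, another reasonable explanation.* It fits Probably.

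For an AE with a rival explanation, then, Probably is the only related level that can be reached. As the PI's suspicion grows, the coding passes from Unrelated or Unknown straight to Probably, with no intermediate step.

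**Step 3. Remove the clause and repeat.** With Possibly defined as a plausible role of study drug that cannot be ruled out, AE 1 fits Possibly. AE 2 stays at Possibly, provided a drug role is plausible, and AE 3 stays at Probably. The exclusion then applies at 1 of 3 levels, the strongest, where it belongs.

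**Step 4. Trace the consequences.**

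- *SAP 7.3.2.* An AE coded Unrelated would be absent from the study-drug-related report. An AE coded Unknown may or may not be, because the SAP does not say which levels count.
- *Protocol 8.2.3.* In either case the AE sits at a level that misdescribes the PI's view in the summary by relationship.
- *Protocol 4.6.* One stopping limb covers AEs of grade 3 or higher judged possibly or likely caused by drug. The text does not tie that phrase to the 9.4.4.2 levels. If investigators apply the same scale there, a grade 3 AE of type 1 could escape that limb. The grade 4, SAE, PI-opinion and liver limbs do not use these levels.

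**The case against.** The strongest defence is that the scale can be read coherently as combining two kinds of evidence: a positive link to the drug, and the absence of another cause. On that reading Possibly has the second without the first, Probably has the first without addressing the second, and Definitely has both. An AE with neither goes to Unrelated or Unknown. This stands. A reader might infer that the scale contradicts itself or that its order is broken, and the text does not support that. The two-axis reading does not remove the gap, however: an AE the PI cannot rule out as drug-caused is still placed outside every related level.

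A reader might also infer that such an AE cannot be coded. It can, because Unknown is an explicit option. But Unknown and Unrelated are both undefined, so two investigators could code the same event differently.

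The hypoglycaemia case has limits. Section 5.8.3 requires permitted drugs to have been at stable doses for at least 3 months before biopsy. A PI could reasonably decide that a long-stable regimen does not explain a new event, which would allow Possibly or Probably. The example shows that the gap can arise, not that it will be common.

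Two further inferences go too far. One is to size the problem by the planned arms of 6, 6 and 3: a single patient is 1/6 = 16.7 percentage points in an active arm and 1/3 = 33.3 on placebo. Those figures hold for reclassifying any one patient on any yes/no outcome and do not measure this defect. The other is that stopping or SAE reporting is compromised. Section 4.6 does not refer to the scale. Section 9.4.2 requires every SAE from consent to 7 days after treatment to be reported within 24 hours regardless of relationship. Only later SAEs depend on a judgement of relatedness, and that text does not refer to the scale either.

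The safeguards are real: all AEs are reported to the sponsor (Protocol 9.4.1) and listed (8.2.3), a DMC reviews safety data (7.4), and with about 15 patients each case can be read individually.

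**Conclusion.** The point holds as a minor defect of wording. It is a stated rule rather than a missing detail, and nothing elsewhere in the protocol or SAP repairs it. Followed literally, it pushes AEs with an uncertain drug link and a rival explanation out of the related levels. The drug-related TEAE report may then be incomplete, and the summary by relationship may place such AEs wrongly.

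The size cannot be given from the documents, and the number of AEs affected may be zero. The conclusion assumes that investigators apply the definitions as written. Any effect on the grade 3 limb of Protocol 4.6 also assumes that they carry the same scale over to that rule. Treatment-emergent AEs remain in the all-TEAE tables whatever their coding, and no efficacy result is touched.

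**What to change.** In Protocol 9.4.4.2, delete the exclusion clause from Possibly related. Define the level as a causal role of study drug that is plausible and cannot be ruled out, whether or not other conditions could also explain the AE. Leave the condition in Definitely related.

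The cost is one clause plus matching eCRF guidance. The downside is that related counts, and possibly grade 3 discontinuations, may be slightly higher, which is the cautious direction for safety. The change acts on AEs coded after it takes effect. Those already coded would have to be reassessed by the investigator, before unblinding, to benefit.

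Which levels SAP 7.3.2 counts as study drug related, and how it treats Unknown or missing, is a separate question. It is worth settling, but counting Unknown as related is debatable and this correction does not need it.
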